### 1. Study Summary

Project Title	Usability of STAR particles in healthy volunteers: A pilot study
Project Design	Non-randomized, controlled, non-blinded, single-arm pilot (feasibility) study, with an adaptative design at mid trial.
Primary Objective	To identify the most efficacious pressure of administration and the minimum number of rubbing cycles necessary to perforate the stratum corneum.
Secondary Objective(s)	To evaluate sensation and pain during and after STAR particle application.
Exploratory Objective(s)	To assess the dispersion and disposal of the STAR particles. To evaluate the user's feedback on product use.
Research Intervention(s)/Interactions	STAR particles STAR particles are millimeter-scale particles with micron-scale projections made of biocompatible materials that painlessly disrupt the stratum corneum. As STAR particles are rubbed on skin, their microscopic projections create micron-scale pores in the stratum corneum to increase skin permeability to topical compounds independent of physicochemical properties. After the arms of the STAR particle puncture the skin, the elastic forces of the skin push the particles out. Participants will receive the 8 interventions (different application pressures) plus the control (Site and treatment will not be randomly assigned on the arm) by the investigator.
Study Population	Adults (18 to 39 years of age)
Sample Size	20
Study Duration for individual participants	1 visit to screen for medical history, examine skin, obtain informed consent, and application of the STAR particles to the participant's forearm.
Study Specific Abbreviations/ Definitions	GV – Gentian Violet; kPa - kilopascal; microneedle (MN); TEWL – trans epidermal water loss; VAPS – visual analog pain scale
Funding Source (if any)	Aldena Therapeutics (United Kingdom)
Study Site	Emory Children's Center

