#### **4. Study Endpoints**

##### **A. Primary**

- 1) For each primary objective, the **primary endpoint** is the identification of the most efficacious conditions measured by the number of perforations per cm^2 using GV staining and TEWL measurement before and after application of STAR particles [(T0 (before), T20 (after), T30, GV)].

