### **B. STAR particle application**

A 1.5 gram dose of STAR particles (10% concentration in gel) will be applied to the eight application sites (forearm and hand) and 100 mg of the gel without STAR particles will be applied to the control site on one of the forearms. Two rubbing cycles (30 and 60 cycles at a minimum of 1 cycle/second) and three pressures (40, 60, and 80 kPa) will be evaluated. The parameters of each STAR particle application at each site (1-9) are labelled in Figure 1. The investigator will apply the STAR particles with two fingers (index and middle fingers of the dominant hand) and the pressure point of one finger is 1 cm^2. Pressures have been established with the following amount of STAR particles applied to the skin with one finger: 40 kPa (320 grams); 60 kPa (480 grams); and 80 kPa (640 grams). With two fingers, the investigator will apply with a pressure of 40 kPa when scale reads 640 grams; 60 kPa = 960 grams; and 80 kPa = 1280 grams. This will be practiced enough before the study so the investigator will know how much pressure generated on the skin based on previous practice with associating pressure according to scale weight.

[figure not shown]

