#### **Application of STAR particles to volar side of each forearm (Figure 1)**

1. Wash participant's arms and hands with disinfecting soap before any application.
2. Allowed skin to dry for at least 10 minutes.
3. Investigator to delimit the 9 areas on participant's forearms and hand with a marker.
4. Measure TEWL  $T_0$  on all 9 sites - measure from areas 1 to 9 and then from 9 to 1, giving 2 measurements for each time point according to Figure 1.
5. Apply STARS (80KPa for 60 cycles) on the dorsum of the closed hand.

6. Apply STARs (80KPa for 60 cycles) to the palmar surface of the same hand.
7. Apply STARs (pressure and # of cycles) to the six areas on the forearms per Figure 1.
8. Extra care will be taken to wash arms and hand with warm water to remove the STAR particles and gel and allowed to dry at least 5 min before the next TEWL ( $T_{20}$ ) is taken.
9. Measure TEWL  $T_{20}$  on all 9 sites - measure from areas 1 to 9 and then from 9 to 1, giving 2 measurements for each time point according to Figure 1.
10. Participant completes Tolerability Questionnaire
11. Participant completes Removal & Disposal Questionnaire and User's Feedback Questionnaire.
12. Pictures (3) will be taken to assess erythema: both forearms and the hand
13. Measure TEWL  $T_{30}$  on all 9 sites - measure from areas 1 to 9 and then from 9 to 1, giving 2 measurements for each time point according to Figure 1.
14. Apply GV staining for 10 minutes on the 2 arms resting with volar arm upward and right hand on a gauze containing GV stain.
15. Wash and wipe off the GV stain thoroughly with ethanol 70%.
16. Take 3 photos of each site to visualize the puncture after GV staining.
17. Using 2 fingers (index and middle), the participant will apply pressure to a kitchen scale in an effort to mimic application of low, medium, and high pressures.
18. The investigator records the weight (from the scale) when the pressure is constant.
19. Participant is discharged.

**Figure 1:** STAR particle application sites for V1 (participants #1-10)

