**Application of STAR particles to volar side of each forearm**

20. Wash participant's arms and face with disinfecting soap before any application.
21. Allowed skin to dry for at least 10 minutes.
22. Investigator to delimit the 9 areas on participant's forearms and face with a marker.
23. Measure TEWL  $T_0$  on all 4 sites - measure from areas 1 to 4 and then from 4 to 1, giving 2 measurements for each time point.
24. Apply STARs (80KPa for 60 cycles) on the forearm.
25. Apply STARs (80KPa for 60 cycles) to the side of the face.
26. Apply gel without STARs on the other forearm and on the other side of the face.
27. The study team will take photos of the application sites.
28. After approximately 5 minutes, the gel (with or without STAR particles) will be removed with a dry tissue or gauze.
29. The study team will take photos of the areas of application.
30. After the gel is removed in all areas, the investigator will examine the participant to check if there are any remaining STAR particles on the participant and/or the surrounding environment.
31. Participant completes Tolerability Questionnaire
32. Participant completes Removal & Disposal Questionnaire and User's Feedback Questionnaire.
33. Pictures (3) will be taken to assess erythema: both forearms and the face
34. Measure TEWL  $T_{30}$  on all 4 sites - measure from areas 1 to 4 and then from 4 to 1, giving 2 measurements for each time point.
35. Apply GV staining for 10 minutes on the 2 arms resting with volar arm upward and right hand on a gauze containing GV stain.
36. Wash and wipe off the GV stain thoroughly with ethanol 70%.
37. Take 3 photos of each site to visualize the puncture after GV staining.
38. Using 2 fingers (index and middle), the participant will apply pressure to a kitchen scale in an effort to mimic application of low, medium, and high pressures.
39. The investigator records the weight (from the scale) when the pressure is constant.
40. Participant is discharged.

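### The stained-perforation count, one of two primary measures, appears to be read from photographs with the setting known; coding and shuffling the images already planned would remove reader bias from it.

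*Protocol*

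**What the plan says.** Protocol section 1 (Study Summary) describes the design as "Non-randomized, controlled, non-blinded, single-arm pilot (feasibility) study, with an adaptative design at mid trial", and section 5 repeats the open-label label. Neither exempts outcome assessment. Section 1 adds: "Site and treatment will not be randomly assigned on the arm". Section 6.B says that the parameters for sites 1 to 9 are labelled in Figure 1, so site identity gives the setting.

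Section 4.A defines the primary endpoint as "the identification of the most efficacious conditions measured by the number of perforations per cm"², obtained by GV staining, together with TEWL before and after application. The settings compared are given in section 6.B: "Two rubbing cycles (30 and 60 cycles at a minimum of 1 cycle/second) and three pressures (40, 60, and 80 kPa) will be evaluated".

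The perforations are recorded at section 6.C step 16, "Take 3 photos of each site to visualize the puncture after GV staining", with the same instruction at section 6.D step 37 for participants 11 to 20. The scale exercise and discharge follow. Nothing in the protocol says who counts, by what rule, or whether that person knows the site. Section 5 provides for an interim analysis after 10 participants, which may change the application area, position, pressure or number of cycles.

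**The concern.** Rubbing at a stated pressure cannot be hidden from the person doing it. Reading a stored close-up can be separated from the application at almost no cost. If a person counts stained marks after the ethanol wipe, some judgement about what is a perforation is likely. If that person also knows the setting, expectation can enter the count.

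The product of this pilot is a choice of setting: the best pressure and the smallest sufficient number of cycles (section 2.A). The choice is first informed by ten participants at the interim analysis. With so few, a small systematic shift in the count at one site could change which setting looks best, or widen or narrow its contrast with the control.

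**Working it through.** **Step 1. Does the site reveal the setting?** Section 1 says allocation is not random, and section 6.B refers to a figure that labels each site's parameters. A reader who can identify the site therefore knows the pressure, the number of cycles and whether it is the control.

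**Step 2. Is the count read from the photographs?** Section 4.A requires a number per cm² from GV staining. The post-stain photographs are the only record of the punctures that section 6 names, and the participant leaves soon afterwards. Counting from the photographs is a strong inference; the text does not state it.

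**Step 3. How many images bear on the choice of setting?**
- Settings compared on the forearms: 2 cycle counts × 3 pressures = 6 (section 6.B). Section 6.C has three particle sites on each forearm, also 6.
- With one forearm control: 6 + 1 = 7 sites.
- Images: 7 × 3 × 10 = 210.
- All nine sites would give 9 × 3 × 10 = 270. The other 2 × 3 × 10 = 60 are hand images. Both hand sites receive 80 kPa for 60 cycles (section 6.C steps 5 and 6), so they compare no settings.
- Participants 11 to 20: four sites would give 4 × 3 × 10 = 120 images. Step 35 stains the arms and a hand although the face is treated. If only the two forearm sites yield stained images, the number is 2 × 3 × 10 = 60.

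**Step 4. How sensitive is a ranking to a reader's lean?** The protocol states no SD, effect size or reader error, so there is no figure to reproduce and the actual bias cannot be derived. As an illustration only, assume:
- six truly equal forearm settings and 10 participants;
- independent normal counts with SD 1 at each site, so each mean has standard error 1/√10 = 0.316 SD;
- a reader who adds *b* SD to one of the six settings.

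In 400,000 simulated runs, the favoured setting ranked first on the count with these frequencies:

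| Assumed lean *b* (SD) | *b* in standard errors | Favoured setting ranks first |
|---|---|---|
| 0 | 0 | 0.17 (1 in 6) |
| 0.1 | 0.32 | 0.24 |
| 0.25 | 0.79 | 0.38 |
| 0.5 | 1.58 | 0.64 |
| 1.0 | 3.16 | 0.95 |

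By symmetry the result is the same whichever setting is favoured. The table ranks on the count alone. TEWL also informs the choice, so it overstates the effect on the final decision to the extent that TEWL is given weight.

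**The case against.** The strongest reply is that the point rests on silence. Calling a trial non-blinded describes the trial; it does not say that image readers are unmasked. Reading rules commonly sit in a statistical analysis plan or reading manual, which is not at hand. Counting from the photographs is itself unstated, and no stain is described as faint or ambiguous. This stands as a limit: masked reading may be planned elsewhere. It does not remove the point, because masking is a design feature that this protocol does state, without exception, and the images needed to mask the reading are already being taken.

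The second reply is TEWL. It is a primary measure in its own right, read by instrument twice per time point in forward and reverse site order, and does not depend on photographs. This stands in full. The weakness concerns the GV count, not the whole endpoint.

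A reader might go further in three ways that the documents do not support:
- **A lean toward high settings.** The step "Apply STARs (80KPa for 60 cycles) on the forearm" for participants 11 to 20 might suggest an expected winner. The design is adaptive after participant 10, and the face sites came in with revision 4.1, so the text does not show whether this was a prior expectation or followed from the first cohort. The objective also seeks the minimum number of cycles, which could pull a reader the other way.
- **A funding motive.** The funder makes the particles, but nothing shows that it would prefer one pressure to another.
- **All nine sites affected alike.** The 60 hand images contrast no settings and cannot be fully masked.

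**Conclusion.** The point holds in limited form. As written, the protocol leaves one of its two primary measures open to reader bias of unknown size and direction in the comparison of six forearm settings and the forearm control, 210 images in the first cohort. This rests on two readings of the text: that the count is made from the post-stain photographs by a person, and that the non-blinded declaration covers that person. Neither is contradicted anywhere in the protocol.

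The simulated frequencies follow entirely from the assumed leans. They show that a ranking based on ten participants is sensitive, not that any lean exists here. The point is worth acting on because the remedy is cheap and the count informs the interim decision.

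**What to change.** Amend section 6.C step 16 and section 6.D step 37 so that:
- GV photographs are taken or cropped as close-ups free of site labels and marker cues;
- files are saved under random codes and shuffled across sites and participants;
- an existing team member who neither applied the particles nor took the photographs does the counting;
- counts are locked before the code is opened, and for participants 1 to 10 this is done before the interim analysis.

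The study can stay open-label in every other respect. If masked reading is already specified in another document, a cross-reference in these steps is enough.

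The cost is file handling and a code list for the 210 forearm images of the first cohort and 60 of the second. No visit, participant procedure or extra reader is added. The limits should be stated with the change: hand and face images remain recognisable by anatomy, and coding does nothing about unmasked, hand-gauged application or the non-random placement of settings on the arm.

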#### D. Participants 11-20

Enrolled healthy adults will receive eight applications (one on the forearm and one on the side of the face of STAR particles and one control application on the other forearm and on the other side of the face).

**Application of STAR particles to volar side of each forearm**

20. Wash participant's arms and face with disinfecting soap before any application.
21. Allowed skin to dry for at least 10 minutes.
22. Investigator to delimit the 9 areas on participant's forearms and face with a marker.
23. Measure TEWL  $T_0$  on all 4 sites - measure from areas 1 to 4 and then from 4 to 1, giving 2 measurements for each time point.
24. Apply STARs (80KPa for 60 cycles) on the forearm.
25. Apply STARs (80KPa for 60 cycles) to the side of the face.
26. Apply gel without STARs on the other forearm and on the other side of the face.
27. The study team will take photos of the application sites.
28. After approximately 5 minutes, the gel (with or without STAR particles) will be removed with a dry tissue or gauze.
29. The study team will take photos of the areas of application.
30. After the gel is removed in all areas, the investigator will examine the participant to check if there are any remaining STAR particles on the participant and/or the surrounding environment.
31. Participant completes Tolerability Questionnaire
32. Participant completes Removal & Disposal Questionnaire and User's Feedback Questionnaire.
33. Pictures (3) will be taken to assess erythema: both forearms and the face
34. Measure TEWL  $T_{30}$  on all 4 sites - measure from areas 1 to 4 and then from 4 to 1, giving 2 measurements for each time point.
35. Apply GV staining for 10 minutes on the 2 arms resting with volar arm upward and right hand on a gauze containing GV stain.
36. Wash and wipe off the GV stain thoroughly with ethanol 70%.
37. Take 3 photos of each site to visualize the puncture after GV staining.
38. Using 2 fingers (index and middle), the participant will apply pressure to a kitchen scale in an effort to mimic application of low, medium, and high pressures.
39. The investigator records the weight (from the scale) when the pressure is constant.
40. Participant is discharged.

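### In participants 11-20 both STAR sites come before the gel-only control sites with no safeguard written between them, so particle carry-over to the controls is not excluded

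*Protocol*

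**What the plan says.** Section 6.D gives participants 11-20 four sites: one STAR forearm, one STAR side of the face, and a gel-only control opposite each. The relevant steps are:

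- Step 20, the only cleaning listed before application, concerns the participant's skin: "Wash participant's arms and face with disinfecting soap before any application".
- Step 24: "Apply STARs (80KPa for 60 cycles) on the forearm".
- Step 25: "Apply STARs (80KPa for 60 cycles) to the side of the face".
- Step 26: "Apply gel without STARs on the other forearm and on the other side of the face".
- Step 28, after all four applications: "After approximately 5 minutes, the gel (with or without STAR particles) will be removed with a dry tissue or gauze".
- Step 30: "After the gel is removed in all areas, the investigator will examine the participant to check if there are any remaining STAR particles". The check also covers the surroundings. No rule is given for a control site found to carry particles.

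On who applies the gel and how, section 6.B says: "The investigator will apply the STAR particles with two fingers (index and middle fingers of the dominant hand". It describes a gel with 10% particles. The Study Summary has participants receive the interventions "plus the control (Site and treatment will not be randomly assigned on the arm) by the investigator". That sentence was written for the eight-intervention layout of participants 1-10.

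Section 4.A bases the primary endpoint on gentian violet perforation counts and on TEWL before and after application. Section 2.C makes particle dispersion an exploratory objective.

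**The concern.** One person goes from two STAR applications of 60 cycles each to the particle-free comparator, and no step written in between would stop particles travelling on the fingers. The STAR gel is also still on the skin at that point, because removal comes two steps later.

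Two things are at stake. First, particles that reach a control site and are rubbed there could raise TEWL, add perforations, or cause redness or sensation, which would make the control look more like the STAR site. Secondly, step 30 looks for stray particles. Particles put on the control side by the investigator's fingers could be counted as spread from the product itself, which confuses the exploratory dispersion objective. This second problem needs no rubbing at the control site.

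**Working it through.** The protocol gives no effect size, standard deviation, power or carry-over figure, so there is no planned figure to reproduce. The check is mainly a reading of the steps in order.

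**1. Is the order fixed?** Yes. Steps 24, 25 and 26 are numbered STAR, STAR, control, with no alternation between participants. The Study Summary says that site and treatment are not randomised. Both control sites (2 of 4 sites) in all 10 participants therefore follow both STAR sites.

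**2. Does anything separate STAR from control?**

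| Possible safeguard | Where | Falls between steps 25 and 26? |
|---|---|---|
| Washing of participant's skin | Step 20 | No, before all applications |
| Alcohol swab of skin | Section 15 | No, before the study |
| Gel removal | Step 28 | No, after all applications |
| Particle check | Step 30 | No, after removal |
| Finger cleaning, new gloves, other applicator | Not listed | Not stated |

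**3. Which measurements could be affected?**

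- TEWL is taken at T0 and T30 on all four sites (steps 23 and 34). Each STAR site therefore has its own baseline, which contamination of a control cannot alter. What is exposed is the STAR-control contrast in change, on forearm and face.
- Gentian violet is applied once, at the end (step 35), to the arms and right hand. No step stains the face, so carry-over could affect this measure at 1 control site, not 2. Staining has no pre-application reading, so for the forearm count the control arm is the only reference.
- Erythema photographs (step 33) and the tolerability questionnaire (step 31) are affected as far as they are read by site.

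**4. What would carry-over do?** Let D be the true STAR-control difference and f the fraction of the STAR effect that also appears at the control. The observed difference is D - fD = (1 - f)D. With f assumed at 5%, 10% and 20%, it becomes 0.95D, 0.90D and 0.80D.

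For scale only, take a two-sided paired t test with n = 10 and alpha 0.05, none of which the protocol specifies as a test. With d the assumed standardised paired difference, power is:

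| d | f = 0 | 5% | 10% | 20% |
|---|---|---|---|---|
| 0.8 | 62% | 57% | 53% | 44% |
| 1.0 | 80% | 76% | 72% | 62% |
| 1.5 | 99% | 98% | 97% | 92% |

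Both f and d are assumptions. The documents support no choice among these values.

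**5. Does the same hold for participants 1-10?** It cannot be shown. Section 6.C announces a control application, but steps 1-19 contain none, so its place in the sequence is unknown.

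**The case against.** The strongest reply is that the protocol is silent on hygiene between sites, which is not the same as saying there is none. Clean hands or fresh gloves may be site routine, and order alone does little harm if they are. This stands: uncleaned fingers are something a reader might infer, but the text does not state it. Nor does it say that the same fingers apply the control gel, since section 6.B describes the two-finger method for STAR particles only.

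A reader might also infer that the contrast must be biased towards no effect. The documents do not support that. The Study Summary says that pores form as particles are rubbed on the skin, and step 26 gives no pressure or cycle count for the control. If the control is not rubbed comparably, the contrast also contains an effect of rubbing, which could widen it. The net direction is open.

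It would also be too strong to call the control the only reference of any kind. TEWL has a baseline at each site, and section 4.A does not define the endpoint as a STAR-control difference. Step 30 might catch gross transfer, though it comes too late to prevent it and leads to no stated action.

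What survives is narrower. The written sequence puts the particle-free comparator last, without a stated safeguard, when the reverse order would remove the question.

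**Conclusion.** The point holds as a weakness in a stated sequence. Carry-over from STAR to control on the investigator's fingers is not excluded in any of participants 11-20. If it occurs and the particles are rubbed in, that component would tend to reduce the STAR-control difference in TEWL on forearm and face, in forearm gentian violet counts and in local tolerability. Particles at a control site could separately be mistaken for dispersion.

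The conclusion rests on two inferences: that the investigator who applies STAR also applies the control in this cohort, and that nothing unwritten separates the two. The size cannot be estimated from the documents, and the 5-20% range only illustrates the arithmetic. The claim does not extend to participants 1-10. The change is still worth making, because it is almost free and carry-over cannot be corrected in the analysis.

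**What to change.** In section 6.D, move step 26 before step 24, so that both gel-only sites are applied first and the STAR sites afterwards. This removes finger carry-over from STAR to control at application by construction. Add a line requiring clean or newly gloved fingers between sites. State also how, and with what, the control gel is applied, since step 26 leaves this open.

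In section 6.C there is no control step to move. When it is written in, place it before step 5.

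The cost is a reordering of existing steps and a glove change or finger clean, with no added visit or measurement. The downside is a few minutes' difference in timing between control and STAR sites. The present order already has such a difference in the opposite direction: two applications of 60 cycles at no less than 1 cycle per second take at most 2 × 60 = 120 seconds of rubbing, plus handling.

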#### **5. Study Intervention/Investigational Agent**

This is a non-randomized, controlled, non-blinded, single-arm pilot study trial, with an adaptive design at mid-trial. After 10 participants complete the study, an interim analysis will be performed and recruitment will either continue with no change to the protocol or, changes may occur in regard to the STAR particle application area, position, pressure, or rubbing cycle in an adaptive design manner.

The trial will be performed in a climatized room and participants will have time to adapt and cool down to decrease risk of modulation TEWL reading.

The investigational agent will be STAR particles made of titanium dioxide, a widely used and safe ceramic material found in sunscreens, cosmetics, and paint. The star-shaped geometry is designed to inhibit complete insertion of the particle into skin, so STAR particles do not remain embedded in the skin. After the arms of the STAR particle puncture the skin, the elastic forces of the skin push the particles out. The STAR particles will be mixed with a gel formulation of the following composition: 0.7%w/w Xanthan Gum + 2.5%w/w Hydroxypropyl methylcellulose + Cyclomethicone and Dimethicone. STAR particles will be produced by Aldena Therapeutics under GMP conditions.

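### For participants 11-20 the protocol does not say how or when the STAR side is chosen, so a choice made after the baseline TEWL reading is not prevented

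*Protocol*

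**What the plan says.** Section 6.D sets up a within-person comparison for participants 11-20: STAR on one forearm and one side of the face, with "one control application on the other forearm and on the other side of the face". The order of the steps is as follows.

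- Step 22 marks the skin: "Investigator to delimit the 9 areas on participant's forearms and face with a marker".
- Step 23 reads T0 TEWL on four sites: "measure from areas 1 to 4 and then from 4 to 1".
- Steps 24 and 25 apply STAR to a forearm and to a side of the face, neither named as left or right.
- Step 26 sets the controls: "Apply gel without STARs on the other forearm and on the other side of the face".

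No figure is cited for these participants. Figure 1, which maps settings to areas, is captioned for participants 1-10. Areas 1 to 4 have no key linking them to a side or a treatment.

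Section 1 describes the study as "Non-randomized, controlled, non-blinded, single-arm pilot (feasibility) study, with an adaptative design at mid trial" and adds "Site and treatment will not be randomly assigned on the arm". Section 5 repeats the description: "This is a non-randomized, controlled, non-blinded, single-arm pilot study trial". Under Section 6.B, "The investigator will apply the STAR particles with two fingers". Section 4.A makes TEWL before and after application, together with perforations counted by gentian violet (GV) staining, the primary endpoint measures.

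**The concern.** A left-right comparison within a person is efficient, but only if the treated side is set without regard to the state of the skin. Here the first step that separates STAR from gel sites follows the baseline reading, and the person applying the product is not blinded. If the side with the lower T0 tended to receive STAR, part of that low reading would be measurement error. The STAR side would then rise towards its usual level by T30 and show a larger increase than the gel side without any effect of the particles. Choosing the higher-T0 side would reverse the sign.

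At stake is the STAR-versus-gel contrast in 10 people, which includes the only controlled face comparison in the study. Analysis cannot reliably repair an unrecorded choice of side, so the visit procedure has to settle it.

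**Working it through.** **What the text fixes.** For participants 1-10, areas are numbered and settings are applied per Figure 1. For participants 11-20, areas are marked (step 22), numbered and read (step 23), and only then assigned to STAR or gel (steps 24-26). No sentence gives the side, the rule, the person or the time. The marking step does not supply a map: it counts 9 areas where the next step counts 4 sites. The supportable statement is that a choice after T0 is possible.

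**Inputs.** From the protocol: 10 participants in this cohort, paired sites, TEWL at T0 and T30. The protocol states no SD, alpha, power or test for this contrast, so there is no figure to reproduce. Everything below is assumed for illustration: a two-sided 5% paired t-test, normal errors, no true STAR effect, one body region.

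**Model.** Let D0 and D1 be the right-minus-left TEWL difference at T0 and T30. Take the SD of D0 as the unit. A share r of its variance persists to T30; the rest is independent error at each time. Let p be the probability that the lower-T0 side receives STAR. The mean of |D0| is √(2/π) = 0.798. Then:

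- bias in the T0-to-T30 change = (2p − 1) × (1 − r) × 0.798
- bias in the T30 value alone = −(2p − 1) × r × 0.798

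**No persistence (r = 0).** If s is the error SD of one reading at one site, the unit is √2 × s, so the mean T0 gap is 0.798 × 1.414s = 1.128s. The standard error of the mean paired difference in change is √4 × s/√10 = 0.632s.

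| p | bias in change | bias / SE | rejection rate (simulated) |
|---|---|---|---|
| 50% | 0 | 0 | 5.0% |
| 60% | 0.226s | 0.36 | 6.4% |
| 75% | 0.564s | 0.89 | 14.2% |
| 100% | 1.128s | 1.78 | 48.4% |

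**Full selection (p = 100%) with persistence,** in units of the SD of D0 (40,000 simulated trials):

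| r | bias in change | rejection, change | bias in T30 value | rejection, T30 value |
|---|---|---|---|---|
| 0.3 | 0.7 × 0.798 = +0.56 | 33% | −0.24 | 11% |
| 0.5 | 0.5 × 0.798 = +0.40 | 23% | −0.40 | 23% |
| 0.8 | 0.2 × 0.798 = +0.16 | 12% | −0.64 | 65% |

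The more stable the left-right difference, the less the change is affected and the more the T30 value is.

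**Always the same side.** This prevents selection on T0. With an assumed systematic left-right difference of 0.5 SD, the change stays unbiased (rejection about 5%), but the T30 value is biased by 0.50 SD (rejection 29% to 30%). GV counts have no pre-application reading, so they behave like the T30 value. This concerns the forearm only, because step 35 stains the arms and right hand and names no face staining.

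**Random 5:5 list fixed before T0.** Bias is about 0 for both measures. Rejection is about 5% with no systematic side difference. With the 0.5 SD difference it is about 5% for the change and 3% for the T30 value.

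**The case against.** A reader might infer from the step order that the investigator picks the side after seeing T0. The documents do not say so. Areas are marked and numbered before any reading, which is equally compatible with a fixed convention that was never written down. That objection stands, and the point is therefore limited to what the text leaves open.

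A reader might also infer that always treating the same side carries any left-right skin difference straight into the result. For the change in TEWL that is wrong, because a stable difference cancels. It is right only for measures taken after application alone.

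The 48% figure likewise belongs to an extreme: full selection and no persistent side difference. Nothing in the protocol suggests such selection or a motive for it, and the test itself is a yardstick supplied here.

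Finally, non-random allocation is a declared choice in a feasibility pilot. That explains why there is no randomization, but it does not say how the side is set. A statement that assignment is not random, made for the arm in the study summary, is not a rule that another team could follow for forearm and face.

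**Conclusion.** The point holds as a gap in the procedure: for participants 11-20 the side rule is unstated, and selection of side after T0 is not prevented in a non-randomized, non-blinded comparison. Whether bias would occur, and how large it would be, cannot be derived from the protocol. Under the assumed worst case the false-positive rate for the TEWL change runs from about 12% (80% of the left-right variance persistent) to 48% (none persistent). Partial selection does much less, at about 6% for 60% selection with no persistence.

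The impact is confined to the STAR-versus-gel contrast in this cohort. It does not reach the objective on pressure and number of cycles, since every STAR site here uses the same setting, 80 kPa for 60 cycles. This is a cheap improvement to a small pilot, not a flaw that undermines it.

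**What to change.** Before participant 11 is seen, draw at random a side list for the 10 participants with STAR on the left in 5 and on the right in 5, separately for forearm and for face. State at step 22 that the side is read from the list and recorded before T0 is measured. Key areas 1 to 4 to side and treatment, and reconcile the count of areas between steps 22 and 23. Compare STAR with gel within participant.

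The cost is a short addition to Section 6.D and a 10-line list, with no added visits, sites or participants. The non-randomized description in Sections 1 and 5 needs a note for side assignment in this cohort. The list works only if it is followed, and it does not address unblinded application, TEWL reading, perforation counting or questionnaires. If the sponsor prefers a fixed side, writing it down would close the selection route, but post-application TEWL values and forearm GV counts would remain open to a systematic left-right difference.
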